**Specific Aim 2: Determine the effect of TUDCA on markers of TGR5 activation.**

*A major strength of this proposal is the systematic and rigorous examination of the molecular mechanisms that are likely to be responsible for the metabolic effects of TUDCA. Our leading hypothesis is that TUDCA enhances insulin sensitivity in skeletal muscle by activating the G-protein coupled cell surface receptor TGR5. This hypothesis will be tested by examining the mRNA expression and protein abundance of TGR5 targets in subjects before and after treatment with TUDCA (or placebo). We will then determine the requirement for TGR5 signaling for the response to TUDCA by using siRNA-based TGR5 silencing.*

In vivo studies: We will evaluate markers of TGR5 activation (PGC-1 $\alpha$ , several genes encoding fatty acid oxidation enzymes, enzymes involved in electron transport, and type 2 deiodinase) in adipose and skeletal muscle tissue samples taken before and after administration of TUDCA at the levels of protein abundance and mRNA expression. Protein will be isolated in the presence of protease and phosphatase inhibitors as described in Aim 1. The protein content and/or phosphorylation status will be performed by using western blotting. The antibodies above are all commercially available and have been used previously by [name] lab (43, 74, 77-80, 82-84). Total RNA will be isolated from tissue biopsies using RNeasy Lysis Buffer as we have described numerous times previously (43, 74, 77-80, 82-84). Quantitative RT-PCR will be performed by using reagents from Applied Biosystems and the ABI 7500 provided by the NORC Adipocyte Biology Core. Muscle mitochondrial DNA content will also be determined by back-extracting total DNA during RNA extraction and measuring the DNA for the mitochondrial gene, Cox1, and normalizing to nuclear DNA content by measuring RPLP0 DNA, which is encoded in the nucleus. Primer sets have been validated to specifically detect mRNAs of interest. *We predict that TUDCA treatment will lead to increased expression and protein abundance of markers of TGR5 activation in human skeletal muscle.*

In vitro studies: If our preliminary data hold true and the analyses described just above show that TUDCA administration activates multiple markers of TGR5 activation, cell biological approaches will be used to determine whether TGR5 is required for the ameliorative effects of TUDCA on insulin signaling and glucose uptake. Human skeletal satellite cells will be isolated and differentiated into myocytes in culture as described in the preliminary data. TGR5, which is well expressed in skeletal muscle cells (44), will then be knocked down by using siRNAs purchased from Sigma. We do not consider this to be a significant

technical hurdle as this technique is used frequently and successfully by [name] and [name] (78, 82-86) and Sigma will continue to provide oligonucleotide siRNA candidates until successful knockdown is achieved. After identifying efficient siRNAs to knockdown TGR5, differentiated myocytes will be treated with siRNAs to TGR5 (or scrambled siRNA control) for 72 h, myocytes will be treated with RTV (or vehicle) with or without pre-treatment with TUDCA as described in preliminary studies. Endpoints will include assessment of protein and mRNA markers of TGR5 activation and ER stress. Subsequent studies will include insulin stimulation to assess phosphorylation of insulin signaling cascade proteins and uptake of 2-deoxyglucose (as described in preliminary studies). *We predict that knockdown of TGR5 will abolish the activation of D2 and other proteins under the control of this signaling pathway. In addition, if TGR5 activation is important to the insulin-sensitizing effects of TUDCA, loss of TGR5 may also attenuate the ability of TUDCA to increase insulin sensitivity in these skeletal myotubes.*

### **Specific Aim 3 Determine the effect of TUDCA on ER stress.**

Alternatively or in addition, we have hypothesized that TUDCA may improve insulin signaling by reducing ER stress, possibly in a cell type-specific manner. To test this hypothesis, we will evaluate markers of ER stress in tissue biopsy samples taken before and after administration of TUDCA. We will also evaluate the direct effects of TUDCA and RTV on these endpoints in adipocytes in culture to begin to dissect the molecular mechanisms involved.

*The proposed methods will examine all three major pathways of the UPR; specifically we will assess 1) activation of PERK by measuring protein abundance of PERK, pEIF2a, EIF2a, and ATF4, 2) ATF6 activation by measuring the protein abundance of ATF6 and 3) Xbp1 splicing by measuring spliced Xbp1 content. We will also assess downstream targets of these pathways by measuring protein content of BIP/Grp78 and activation of the JNK pro-inflammatory pathway by measuring phosphoJNK.*

In vivo studies: ER stress markers will be quantified in adipose tissue and skeletal muscle of study subjects. Protein and RNA will be isolated as described above and markers evaluated by using western blotting and qRT-PCR. We will assess various markers by protein abundance or phosphorylation status (BIP/Grp78, Grp94, pEIF2a/EIF2a, IRE-1, PERK, spliced Xbp1, Chop, ATF6, ATF4, and phosphoJNK). The splicing of Xbp1, which is increased by ER stress will be assessed by using SYBR chemistry quantitative reverse transcriptase-PCR (Applied Biosystems). Relative abundance calculated using the delta-Ct method ( $2^{-\Delta Ct}$ ) with a housekeeping gene (RPLP0). Total RNA will be extracted from frozen muscle and adipose biopsy samples as described (87). Adipose tissue samples taken before and after the intervention will be analyzed for macrophage and inflammatory gene expression (IL-6 and TNF- $\alpha$  expression, F4/80, CD68, EMR1, CD11b, MIP-1a, CCL3-R) to determine if administration of TUDCA affects markers of adipose tissue inflammation. We predict that treatment with TUDCA will reduce signs of ER stress in adipose tissue, but not skeletal muscle, of study subjects treated with PI-ART.

In vitro studies: If, as predicted, TUDCA reduces ER stress in adipose tissue above, the effects could be direct effects of TUDCA as a chemical chaperone in adipocytes or could be secondary to systemic improvements in insulin sensitivity and metabolism. To address this issue, the human adipocyte cell line (Lisa-2; provided by the NORC ABC) will be cultured and differentiated in vitro. Adipocytes will then be treated with RTV and/or TUDCA as described for the human skeletal myocytes in prelim studies. Endpoints will include markers of ER stress, insulin signaling, and 2-DG uptake. Based on preliminary studies and published work showing that PI-ART activates ER stress in adipocytes (19, 88, 89) we predict

that treatment of adipocytes with RTV will activate the ER stress response and impair insulin signaling and glucose uptake and that TUDCA will attenuate or reverse these effects of RTV.

Finally, it is also possible that the ability of TUDCA to ameliorate ER stress could be blocked by loss of TGR5 signaling. Though this would seem to be a more unlikely possibility, the mechanism whereby TUDCA ameliorates ER stress is not known, and could involve TGR5 signaling. To test this idea, TGR5 will be knocked down by using siRNA (as described for myocytes) and the ability of TUDCA to ameliorate ER stress and improve insulin responsiveness in adipocytes will be examined. These mechanistic studies would provide a significant conceptual advance for the field by establishing the mechanism whereby these effects occur.

## E 2.C

**Randomization.** Participants will be randomized to TUDCA or placebo. A computer-based randomization scheme will be established, as used in our prior research protocols (90) and *group assignment will be stratified by race and gender. The study statistician, [name], who will be unblinded to group assignment, will provide ongoing oversight to ensure groups are well matched on key characteristics (age, BMI, race, gender).* Capsules containing TUDCA and matching placebo will be made by our research pharmacy, as has been performed in our other placebo-controlled studies (90). The PI, subjects and research technicians will be blinded with respect to group assignment. The coordinator will also be unblinded to group assignment. In the event of an adverse event the coordinator will inform the team and subject of group assignment. [name] RN and [name] RN will be unblinded to ensure that group assignment is known in the case a subject requires urgent medical care.

**Sample Size and statistical power:** All power computations are based on two-sided tests at the 0.05 level of significance for the *primary outcomes* of change of 1) insulin-stimulated glucose disposal (**SA#1**), 2) type 2 deiodinase expression in skeletal muscle (**SA#2**) and 3) Grp78 expression in adipose tissue (**SA#3**) after the intervention.

*Significance of primary outcomes:* Change in insulin-stimulated glucose disappearance is clinically relevant as a predictor of diabetes risk and is highly reproducible in our hands, improving statistical power (91). D2 and Grp78 expression are robust markers of TGR5 activation and ER stress, respectively, and will therefore clarify the mechanisms through which TUDCA may act to improve insulin sensitivity.

*Estimates of change in the primary outcomes:* The estimates for the anticipated changes in the primary endpoints of glucose disposal and D2 expression are based on the prior study conducted in obese, insulin resistant subjects. In this study, glucose rate of disappearance improved by  $30\pm 23\%$  and D2 expression in muscle increased  $2.4\pm 2.5$  fold (Fig 10) after the TUDCA intervention (43). The estimate for the change in Grp78 expression following initiation of TUDCA is based on improvements seen in animal studies with use of TUDCA (52, 53) and in humans after undergoing gastric bypass (92). Based on these findings we estimate a  $50\pm 25\%$  change in Grp78 in the TUDCA group with no change in the placebo group.

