### **3. Screening studies** (Performed at WUSTL and VUMS-ACTU)

*Medical examination.* All subjects will be screened with a detailed history and physical examination, pregnancy test (*if female*) and CBC, lipid profile, liver panel and resting 12-lead electrocardiogram. CD4 T-cell count, and plasma viral load. *Oral glucose tolerance test.* After an overnight (12 h) fast, blood samples for plasma glucose, and insulin will be obtained immediately before and every 30 min for 2 h after ingesting a 75 g oral glucose load. The criteria of the Expert Committee on the Diagnosis and Classification of Diabetes Mellitus (67) will be used to determine diabetes. Other than these screening procedures, all other components of the study are performed at WUSTL.

Eligible subjects from VUMS-ACTU who are consented and are eligible will be discussed by the research team at VUMS-ACTU and the study PI, [name]. If the subject meets eligibility criteria transport will be arranged by WUSTL for the patient to undergo body composition, assessment of intramyocellular and intrahepatic TG content and the inpatient isotope-infusion protocols at WUSTL. After completion of baseline inpatient testing they will be kept overnight and transported back to Nashville the following day. All eligible subjects will undergo baseline testing within 3 months of screening. Subjects will have their study medication dispensed at WUSTL and both WUSTL and the VUMS-ACTU will have a staff member ([name], not involved in data analysis) unblinded to group assignment for safety. Subjects enrolled at VUMS-ACTU will return to VUMS-ACTU every ~7 days for a pill count, vital signs, and to assess for any medication intolerance or other AEs.

*Body Composition and assessment of intramyocellular and intrahepatic TG content:* Body composition will be measured within a week of the isotope infusion protocol. Total body fat and fat-free mass will be determined by dual energy x-ray absorptiometry (DXA) (Hologic QDR 4500, Waltham, MA) (68). Abdominal (subcutaneous and intra-abdominal) adipose tissue mass will be quantified by magnetic resonance imaging (69, 70). Intrahepatic TG content will be determined by proton MRS (3T whole-body system; Magnetom Vision Scanner; Siemens, Erlanger, Germany) as previously described (71).

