## 5. Isotope-Infusion Protocols.

*Pre-study dietary intake and physical activity.* All subjects will be instructed to abstain from any exercise and to ingest a standard weight-maintaining diet for three days before the isotope infusion protocol. Our study dietician will give dietary instructions individually to each subject. Each subject will keep a complete 3-day food log to judge compliance. The diet will contain at least 300 g of carbohydrate/day and the relative contributions from protein, carbohydrate, and fat will be approximately 15%, 55%, and 35% of calories, respectively. On the third day of the diet, subjects will be admitted to the IRU at 1600 h and their 3-day diet records will be reviewed. If their diet is inappropriate (e.g. inadequate in carbohydrate or energy intake) the study will be rescheduled. The study's dietary counselor will provide counseling by phone to participants recruited from the Vanderbilt site.

*Hyperinsulinemic euglycemic clamp.* Subjects will be admitted to the Clinical Research Unit (CRU) for isotope infusion studies to assess insulin sensitivity in liver, adipose tissue and skeletal muscle (Fig 12). At 1800 h on the day of admission, subjects will be given a standard meal (containing 15 kcal/kg FFM), which will be consumed by 1900 h. Subjects will then receive a can of Boost™. After this meal, subjects will fast until completion of the isotope infusion studies the following day. At 0500h, a catheter will be inserted into the antecubital vein of the arm to infuse isotope tracers and another catheter will be placed in the contralateral dorsal hand vein. The hand will then be placed in a thermostatically controlled box heated to 55C to obtain arterialized blood samples. If a hand vein cannot be cannulated, a radial arterial line will be placed. We have found that a radial artery catheter is well tolerated by study subjects, and ensures rapid and secure blood sampling. We now have inserted hundreds of catheters without any complications.

Tauroursodeoxycholic acid for protease-inhibitor associated insulin resistance  
 PI: [name]

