**Adequacy of protection against risks.** All experimental procedures will be explained in writing and orally to the subject by the principal investigator, co-investigator, or the research coordinator. Written informed consent will be obtained after all questions have been answered and the risks and benefits of participation in the study have been described. The objectives of the project, all of the requirements for participation, and any possible discomforts and risks will be clearly explained to each subject orally and in writing in lay terms that he/she is able to comprehend. The subject must sign a consent form, approved by the Washington University School of Medicine Institutional Review Board, before participating in any aspect

of the study. To secure data transfer between WUMS and VUMS, a Secure File Transfer system will be used to transmit any PHI or study-related data. An original copy of each consent will be kept on file at the primary site with an additional signed consent at VUMS. At each site all data will be kept within a secure server and will be deidentified at the closure of the study.

**H2 Compliance Program:** During the intervention, subjects will be seen weekly by a member of the research team who will take weight, measure blood pressure and pulse, review any problems and verify compliance by using a pill count. Should the need for medical evaluation arise, they will be seen by the PI, [name], [name], [name] all of whom are certified in Internal Medicine.

Should the need for medical attention arise all the resources of a large teaching hospital at each site are available for subject evaluation and treatment. Complete physical examinations will be performed to screen out subjects who may be at potential risk. Subjects will be carefully monitored by the medical staff associated with the study for the duration of the study.

Potential benefits of the proposed research to the subjects and others. Potential benefits to the subjects participating in the study include information regarding their medical health, and screening for diabetes. Benefits to society include a better understanding of the factors responsible for insulin resistance in HIV and the mechanisms through which bile acids may improve these outcomes.

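### As written, any adverse event, however mild, triggers disclosure of the assignment to the subject and the team; no condition of seriousness or clinical need is stated

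*Combined protocol and SAP*

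**What the plan says.** Section E 2.C (Randomization) sets the blind: "The PI, subjects and research technicians will be blinded with respect to group assignment". The coordinator is unblinded. The disclosure rule follows: "In the event of an adverse event the coordinator will inform the team and subject of group assignment". The next sentence names two nurses who "will be unblinded to ensure that group assignment is known in the case a subject requires urgent medical care".

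Section 3 (Screening studies) adds that each site has a staff member, not involved in data analysis, who is "unblinded to group assignment for safety". It also has subjects enrolled at the second site return about every 7 days, among other things "to assess for any medication intolerance or other AEs". H2 (Compliance Program) provides that, during the intervention, "subjects will be seen weekly by a member of the research team", with a review of any problems. On medical evaluation it says: "Should the need for medical evaluation arise, they will be seen by the PI", and then lists further physicians. H3 (Data and safety monitoring) has the PI, research nurse and coordinator review serious adverse events, adverse events and laboratory values.

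**The concern.** A code-break rule in a double-blind trial normally turns on whether someone needs the assignment to treat the subject. Here the trigger is the occurrence of an adverse event, the instruction is that the coordinator will disclose, and the recipients include the subject. A mild, self-limiting complaint meets that trigger.

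Subjects could therefore learn their assignment before the final clamp. Because the team is undefined, the PI and technicians, whom the same section blinds, might learn it too. Knowing the assignment could affect adherence, drop-out or conduct at later visits. The plan describes no record of code breaks, so a reader of the results could not tell how much of the blind had survived.

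**Working it through.** No arithmetic applies. The plan gives no adverse event rate for this trial, so there is no figure to reproduce. The check is whether any text limits the rule in E 2.C.

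1. **The trigger.** The sentence refers to an adverse event without qualification. It gives no grade, seriousness, relatedness or clinical-management condition, and the verb is mandatory.

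2. **Could the term mean a serious event?** H3 lists serious adverse events and adverse events as separate categories. Section 3 treats medication intolerance as one kind of adverse event. The unqualified term is therefore not the protocol's shorthand for a serious one.

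3. **Does the urgent-care wording limit disclosure?** It explains why two nurses hold the code. It does not say when the coordinator may release it. The same is true of the safety wording in Section 3, which gives a reason for holding the code and no release criterion.

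4. **Does the safety section limit it?** H1 to H3 cover risks, weekly contact, review and reporting of events, and access to the monitoring board. None of them addresses breaking the code.

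5. **Would mild events meet the trigger?** D.2 gives diarrhea, headache, dyspepsia and abdominal pain as the main reported side effects and describes the diarrhea as mild. H1 lists pain and bleeding from the biopsies as risks. Problems are asked about weekly, so such events are likely to be picked up if they occur. The exclusion of persistent diarrhea in E 2.b applies at entry and does not cover diarrhea that starts on treatment.

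6. **Who would be told?** The subject, explicitly. The PI and technicians, possibly. H3 has the PI reviewing all adverse events with the coordinator, and H2 names the PI first among the physicians who see subjects. This makes it plausible, though not certain, that the PI belongs to the team.

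7. **How many?** This cannot be determined. D.2 cites a study of 10 obese, insulin-resistant adults on the same daily dose for 4 weeks with no adverse events. B1 describes that population as HIV-uninfected, so it does not supply a rate for this trial.

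**The case against.** The strongest reply is that the rule was meant as an emergency code break. The surrounding text speaks of safety and urgent care, and a fully literal reading has ordinary biopsy pain ending the blind, which is hard to square with a double-blind trial. That is a fair account of likely intent. It also shows how loose the wording is, and staff following the sentence as written would disclose.

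A second reply is that disclosure has a safety purpose. This stands. The sentence is the only disclosure instruction in the plan, and unblinded nurses help only if someone may release the code. H1 also says that the effect of TUDCA on the absorption and handling of antiretroviral drugs is unknown, so a treating clinician may need the assignment. The objection is to routine disclosure, especially to the subject, and not to having a code break.

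Third, the consequences are probably small. The outcomes are tracer and laboratory measurements, treatment lasts 30 days, pill counts are weekly, and subjects are told to "abstain from any exercise and to ingest a standard weight-maintaining diet for three days" before each infusion study. A side effect can also prompt drop-out or a guess at the assignment under any rule, so only the added effect of disclosure counts. This also stands.

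A reader might infer that unblinding would be concentrated in the TUDCA arm, because the listed side effects are drug-related. The documents do not establish this. They give no event rates by arm, and procedure-related events such as biopsy pain would arise in both arms.

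**Conclusion.** The point holds as a defect in a stated rule. The protocol blinds the PI, subjects and technicians, and two sentences later requires disclosure after any adverse event, with no limit there or elsewhere. This is more than missing detail, because an instruction is given and following it would give up part of the blind for minor reasons.

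A reader might go further and infer that the primary comparison would be biased or the trial effectively open-label. The documents do not support that. The number of subjects affected is unknown and could be zero. Nothing in the documents shows that learning the assignment changes adherence, retention or the measured outcomes, and any effect on the tracer and laboratory endpoints is probably small. Nor can it be said that the PI would certainly be unblinded.

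The conclusion rests on the literal wording, on the protocol's own separation of adverse events from serious ones, and on the absence of a limiting condition in the text on blinding and safety. It is worth fixing because the correction is simple and protects a stated design feature, not because a large effect has been shown.

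**What to change.** Replace the disclosure sentence in E 2.C with a rule along these lines:

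- The code is broken only when knowing the assignment is needed for a subject's medical care.
- The coordinator or nurses who are already unblinded release it to the clinician treating that event, who should be a physician other than the PI where possible. H2 lists others besides the PI.
- The subject, the PI and the technicians otherwise stay blinded.
- Each break is logged with its date and reason, and breaks are reported by arm.

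The cost is one changed sentence, the usual ethics-board amendment and a short log. The unblinded roles already exist. The downside is that a subject with a mild event is not told the assignment during the trial. If the intent was always emergency-only, the change puts that intent in writing.
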